11.2.5 Progression-Free Survival (PFS)

Interval of time between date of initiation of protocol treatment and minimum date of documentation of PD, death due to any cause, or date of last follow-up.

12 Data Reporting/ Regulatory Requirements

Adverse event lists, guidelines, and instructions for AE reporting can be found in Section 7 (Adverse Events: List and Reporting Requirements).

12.1 Data Reporting

Medidata Rave is a clinical data management system being used for data collection for this trial. Access to the trial in Rave is controlled through the CTEP-IAM system and role assignments.

Requirements to access Rave via iMedidata:

- A valid CTEP-IAM account; and
- Assigned a Rave role on the PBTC roster at the enrolling site of: Rave CRA, Rave Read Only, Rave CRA (LabAdmin), Rave SLA, or Rave Investigator.

Rave role requirements:

- Rave CRA or Rave CRA (Lab Admin) role must have a minimum of an Associate Plus (AP) registration type;
- Rave Investigator role must be registered as an Non-Physician Investigator (NPIVR) or Investigator (IVR); and
- Rave Read Only role must have at a minimum an Associates (A) registration type.

Refer to <https://ctep.cancer.gov/investigatorResources/default.htm> for registration types and documentation required.

Upon initial site registration approval for the study in Regulatory Support System (RSS), all persons with Rave roles assigned on the appropriate roster will be sent a study invitation e-mail from iMedidata. To accept the invitation, site staff must log in to the Select Login (<https://login.imedidata.com/selectlogin>) using their CTEP-IAM username and password and click on the *accept* link in the upper right-corner of the iMedidata page. Site staff will not be able to access the study in Rave until all required Medidata and study specific trainings are completed. Trainings will be in the form of electronic learnings (eLearnings) and can be accessed by clicking on the link in the upper right pane of the iMedidata screen. If an eLearning is required and has not yet been taken, the link to the eLearning will appear under the study name in iMedidata instead of the *Rave EDC* link; once the successful completion of the eLearning has been recorded, access to the study in Rave will be granted, and a *Rave EDC* link will display under the study name.

Site staff that have not previously activated their iMedidata/Rave account at the time of initial site registration approval for the study in RSS will receive a separate invitation from iMedidata to activate their account. Account activation instructions are located on the CTSU website in the Data Management section under the Rave resource materials (Medidata Account Activation and Study Invitation Acceptance). Additional information on iMedidata/Rave is available on the CTSU members' website in the Data Management > Rave section at www.ctsu.org/RAVE or by contacting the CTSU Help Desk at [name] or by e-mail at [contact].

12.2 Method

This study will be monitored using CDUS-Abbreviated reporting, and as such no adverse event reporting (routine or expedited) is required to be reported via CDUS.

12.3 Responsibility for Data Submission

The OBDMC for the PBTC is responsible for compiling and submitting CDUS data to CTEP for all participants and for providing the data to the Principal Investigator and sponsor for review.

12.4 CTEP Multicenter Guidelines

The specific responsibilities of the Principal Investigator and the Coordinating Center:

- The Principal Investigator/Coordinating Center is responsible for distributing all IND Action Letters or Safety Reports received from the pharmaceutical company to all participating institutions for submission to their individual IRBs for action as required.
- Except in very unusual circumstances, each participating institution will order agents directly from the Secura Bio Inc. Agents may be ordered by a participating site only after the initial IRB approval for the site has been forwarded by the Coordinating Center to the sponsor.

12.5 Collaborative Agreements Language

A Clinical Trial Agreement will be in place to document study operations between Secura Bio Inc. and the PBTC. A Materials Transfer Agreement will be in place to document correlative study operations between the applicable labs and analyzing centers, and the PBTC.

12.6 Genomic Data Sharing Plan

Unlinked genomic data will be deposited in public genomic databases such as dbGaP in compliance with the NIH Genomic Data Sharing Policy.

13 Statistical Considerations

[figure not shown]
13.1 Study Design/Endpoints

Six dose levels are proposed and all may or may not be investigated, primarily dependent upon whether or not toxicity at dose level 1 results in de-escalation to dose level 0. Enrollment will commence at dose level 10mg/m² for Stratum 1 and at 1 dose level above the Stratum 1 MTD/RP2D in Stratum 2. If the ‘3 weeks on, 1 week off’ schedule is abandoned in Stratum 1 without determining the MTD, then we will initiate dose escalation in Stratum 2 at 10mg/m². Dose finding will be governed by a two stage continual reassessment method (CRM) which will be applied separately in the two strata. No intra-patient dose escalations will be allowed.

13.1.1 Proposed Dose Levels and BSA Based Dosing

Since panobinostat is an oral agent and supplied in fixed capsule sizes, the deliverable doses based on BSA considerations are limited to the rounding constraints as set by the minimum capsule size. Taking this into consideration along with the starting dose of 10mg/m² in Stratum 1 we developed an algorithm that enabled us to choose dose levels that would avoid overlaps in BSA adjusted doses in our patient cohorts. The following plot illustrates the BSA adjusted doses that the patients would receive at the proposed dose levels based on a minimum capsule size of 5mg. For the lower dose levels we have also utilized minimum BSA restrictions for enrollment to avoid these overlaps. Dosing nomograms are provided in **Appendix D: Dosing Tables** to facilitate correct dosing of patients based on this approach.

Figure 2: BSA Adjusted Doses vs. Body Surface Are for the Proposed Dose Levels

13.1.2 Dose Finding Algorithm

Likelihood Based 2-Stage CRM:

In this trial we will use the likelihood-based 2-stage CRM^{71,72,73} as the dose finding algorithm for estimating the MTD. We will use the *dfcrm* package⁷¹ available in R to operationally execute this approach. The toxicity probability of 0.25 is determined as the target probability to be associated with the MTD for both strata. That is, the MTD is defined as the dose at which the model estimates that 25% of patients would be expected to experience dose-limiting toxicities (DLT).

With pre-determined dose levels to be investigated, the practical implementation is to call the “MTD” the proposed dose level nearest to the value identified by the model (dose-finding MTD). The trial will continue until the MTD recommendation can be made based on at least 6 patients treated at that dose level; the model recommends a level lower than the lowest proposed level; or 6 patients have been studied at the highest pre-determined dose level and the model suggests escalation. In the event that the model recommends a level lower than the lowest proposed level or 6 patients have been studied at the highest pre-determined dose level and the model suggests escalation, an estimate of the MTD will not be available, though a Phase II dose may still be recommended utilizing also the available PK and clinical data. If the trial results in an MTD, the reports of this study will include the model estimated MTD as well as the “dose-finding MTD” based on the fixed proposed levels.

We will initiate the dose finding algorithm, so called the *first-stage*, using an empirical approach until the first DLT is observed. Once the first DLT is observed, we will switch to a CRM design (*second stage*) and will use a likelihood-based algorithm to guide dose finding. Since we are using

a likelihood based approach, the use of the first stage is needed as the model cannot estimate the MTD unless some heterogeneity is observed in the toxicity outcomes i.e. at least 1 DLT and 1 non-DLT.

Details of the Dose Finding Algorithm for Stratum 1:

First Stage:

We will initiate enrollment at dose level 1 and in the absence of any DLTs we will enroll the following numbers of patients at each dose level. This enrollment sequence has been shown to be coherent⁷¹ for the target probability of 25%. Note that enrolling 3 patients at dose level 1 would make this enrollment sequence non-coherent:

Planned Enrollment per Dose Level in the absence of any DLTs

Dose level	0	1	2	3	4	5
Number of Patients to be Enrolled	0	2	3	3	3	6

Until the first DLT is observed, using an approach similar to empirical methods e.g. 3+3 or Rolling-6, we will make the above-described number of slots available at each dose level and will wait until all patients have completed the DLT assessment before escalating to the next dose level. In the absence of a DLT in the prior dose levels, once we reach the highest dose, we will make 6 slots available.

Second Stage:

Once the first DLT is observed, we will switch to a CRM design (*second stage*) and will use a likelihood-based algorithm via the empiric function (also called the power function, $F(x, \beta) = x^\beta$ for $0 < x < 1$) to guide dose finding. This function has been shown to perform well under a wide variety of scenarios using the two-stage CRM. Following the detailed guidance in Cheung et al, 2011⁷¹ and using 25% as target probability for the MTD, we have calibrated this design via the following statistical parameters:

- An indifference interval was defined with a half width of 7% i.e. if the model identifies a dose as the MTD in the interval 18% to 32% ($25\% \pm 7\%$), the investigators will be indifferent to this choice.
- Dose level 3 is chosen as the initial guess for the MTD in line with the recommendations in Cheung et al, 2011⁷¹.
- Based on the above assumptions, the skeleton (initial guesses for the toxicity probabilities) is estimated as the following:

The initial toxicity probability assumptions (the skeleton)

Dose level	0	1	2	3	4	5
Toxicity probability	0.02	0.05	0.13	0.25	0.40	0.54

- MTD will be declared as the dose level at which at least 6 patients have been treated and the algorithm does not recommend escalation or de-escalation.
 - o Once the MTD is declared or the Phase II recommended dose is identified, we will enroll 6 additional patients at this dose level to better characterize the toxicity and pharmacokinetic profile of this dose level. We will monitor the DLTs in this

expanded cohort in a similar fashion and if the toxicities in this expanded cohort suggest that the initially declared MTD may be too toxic, we will reduce the dose level and study additional patients at the lower dose until 12 patients have been treated at this dose level and the model does not suggest de-escalation.

While the purest form of the CRM calls for fully sequential dose assignments, we will implement some restrictions in an effort to be conservative in dose escalations:

- We will escalate 1 dose level at a time without skipping doses.
- Once the second-stage is initiated, at each new dose level three slots will be made available and we will require that all patients complete the DLT assessment before additional patients can enroll. Furthermore, we will restrict enrollment so that no more than 3 patients will have DLT evaluation pending at any given point in time.
- Once a dose level has been visited once and 2 evaluable patients have been treated there, subsequent patients will be assigned to the dose level closest to the current estimate of the MTD without skipping a level, if the decision is to escalate. In the event that the model recommends de-escalation, skipping dose levels is permitted. If the first dose level (dose level 1) is found to have unacceptable toxicity, additional patients will be treated at dose level 0.
- It is typical to encounter study eligible patients who are initially enrolled to the dose-finding phase and are later deemed inevaluable for dose-finding for some reason, such as incomplete course of treatment. Our version of the CRM requires that at least two patients are not only enrolled at a given previously unstudied dose level but are also evaluable for dose-finding. If two patients are enrolled to a level and one is deemed inevaluable for dose-finding, then the inevaluable patient must be replaced to ensure that at least two evaluable patients have been treated at that level, regardless of the outcome of the evaluable patient, unless the algorithm recommends de-escalation following a DLT outcome from the first patient.
- Per CTEP's recommendation we will also employ the following 2 restrictions in an attempt to minimize exposure of patients to dose levels that may be too toxic:
 - o New patients will not be assigned to a dose level **above** a dose level where $\geq 33\%$ of patients have experienced a DLT.
 - o New patients will not be assigned to a dose level **at which** 4 or more patients have been treated and $\geq 33\%$ of the patients have experienced a DLT.

Details of the Dose Finding Algorithm for Stratum 2:

First Stage:

We will initiate enrollment 1 dose level above the highest safe dose studied in Stratum 1 (denoted generically as dose level 1 below) and in the absence of any DLTs we will enroll the following numbers of patients at each dose level.

Planned Enrollment per Dose Level in the absence of any DLTs

Dose level	1	2	3	4
Number of Patients to be Enrolled	3	3	3	6

Until the first DLT is observed, using an approach similar to empirical methods e.g. 3+3 or Rolling-6, we will make the above-described number of slots available at each dose level and will wait until all patients have completed the DLT assessment before escalating to the next dose level. In the absence of a DLT in the prior dose levels, once we reach the highest dose, we will make 6 slots available.

Second Stage:

Once the first DLT is observed, we will switch to a CRM design (*second stage*) and will use a likelihood-based algorithm via the empiric function (also called the power function, $F(x, \beta) = x^\beta$ for $0 < x < 1$) to guide dose finding. This function has been shown to perform well under a wide variety of scenarios using the two-stage CRM. Following the detailed guidance in Cheung et al, 2011⁷¹ and using 25% as target probability for the MTD, we have calibrated this design via the following statistical parameters:

- An indifference interval was defined with a half width of 7% i.e. if the model identifies a dose as the MTD in the interval 18% to 32% (25%±7%), the investigators will be indifferent to this choice.
- Dose level 2 is chosen as the initial guess for the MTD in line with the observed toxicity information from Stratum 1
- Based on the above assumptions, the skeleton (initial guesses for the toxicity probabilities) is estimated as the following:

The initial toxicity probability assumptions (the skeleton)

Dose level	0	1	2	3	4
Toxicity probability	0.05	0.13	0.25	0.40	0.54

- MTD will be declared as the dose level at which at least 6 patients have been treated and the algorithm does not recommend escalation or de-escalation.
 - o Once the MTD is declared or the Phase II recommended dose is identified, we will enroll 6 additional patients at this dose level to better characterize the toxicity and pharmacokinetic profile of this dose. We will monitor the DLTs in this expanded cohort in a similar fashion and if the toxicities in this expanded cohort suggest that the initially declared MTD may be too toxic, we will reduce the dose level and study additional patients at the lower dose until 12 patients have been treated at this dose level and the model does not suggest de-escalation. If the accrual is slow and the expansion cohort does not reach 12 subjects in a reasonable time and if the DLT outcome of the additional patients will not affect the MTD estimate, enrollment may be declared as complete. This decision will be made by the study team, IND Sponsor and the PBTC leadership in collaboration with the PBTC DSMB.

While the purest form of the CRM calls for fully sequential dose assignments, we will implement some restrictions in an effort to be conservative in dose escalations:

- We will escalate 1 dose level at a time without skipping doses.
- Once the second-stage is initiated, at each new dose level three slots will be made available and we will require that all patients complete the DLT assessment before additional patients can enroll unless the DLT information from the pending patients do not change the escalation/de-escalation decision.

- Once a dose level has been visited once and at least 2 evaluable patients have been treated there, subsequent patients will be assigned to the dose level closest to the current estimate of the MTD without skipping a level. If the first dose level (dose level 1) is found to have unacceptable toxicity, additional patients will be treated at dose level 0.
- It is typical to encounter study eligible patients who are initially enrolled to the dose-finding phase and are later deemed inevaluable for dose-finding for some reason, such as incomplete course of treatment. Our version of the CRM requires that at least two patients are not only enrolled at a given previously unstudied dose level, but are also evaluable for dose-finding. If two patients are enrolled to a level and one is deemed inevaluable for dose-finding, then the inevaluable patient must be replaced to ensure that at least two evaluable patients have been treated at that level, regardless of the outcome of the evaluable patient, unless the algorithm recommends de-escalation following a DLT outcome from the first patient.
- Per CTEP's recommendation we will also employ the following 2 restrictions in an attempt to minimize exposure of patients to dose levels that may be too toxic:
 - o New patients will not be assigned to a dose level **above** a dose level where $\geq 33\%$ of patients have experienced a DLT.
 - o New patients will not be assigned to a dose level **at which** 4 or more patients have been treated and $\geq 33\%$ of the patients have experienced a DLT.

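### Stratum 2's no-skip sentence has lost Stratum 1's limitation to escalation, so read literally it also stops the CRM from stepping down more than one level

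*Combined protocol and SAP*

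**What the plan says.** All references are to Section 13.1.2 of the combined protocol and SAP unless stated.

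- **Target and model.** "The toxicity probability of 0.25 is determined as the target probability to be associated with the MTD for both strata". After the first DLT the plan "will use a likelihood-based algorithm via the empiric function" (the power model). For Stratum 2, "Dose level 2 is chosen as the initial guess for the MTD", the indifference interval is 18% to 32%, and the skeleton for levels 0 to 4 is printed as "Toxicity probability 0.05 0.13 0.25 0.40 0.54".
- **Stratum 1 restrictions.** The no-skip clause on assignment carries a condition confining it to decisions to escalate. The next sentence reads "In the event that the model recommends de-escalation, skipping dose levels is permitted". The list also requires that "no more than 3 patients will have DLT evaluation pending at any given point in time".
- **Stratum 2 restrictions.** The matching bullet states that "subsequent patients will be assigned to the dose level closest to the current estimate of the MTD without skipping a level" and ends there. It has no escalation condition and no permission to skip downward. The cap of three pending evaluations is also absent. Where it stood, the bullet on waiting for DLT results has an exception for pending results that could not alter the dose decision. That waiting rule is written for newly opened levels.
- **Common to both.** A first bullet limits escalation to one level at a time. Two restrictions recommended by CTEP bar assignment above a level with at least 33% DLTs, and at a level with four or more treated and at least 33% DLTs. Each list is introduced as a way of being cautious when escalating.

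**The concern.** The two lists are parallel, and no reason is given for the difference. A bar on skipping is protective on the way up. On the way down it works the other way: when toxicity is much worse than expected and the model points two levels lower, the literal wording keeps the next child on the level in between. An executable dose-assignment rule should not depend on the reader guessing that a qualifier was left out.

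The pending limit is a separate and lesser matter. It does not determine which level is assigned. It determines how many children can be under observation at once at a level that is not new, including the six-patient expansion.

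**Working it through.** **1. Reproduce the plan's skeleton.** Inputs: target 0.25, half-width 0.07, prior MTD at level 2 (third of five modelled levels). The standard indifference-interval recursion gives 0.0505, 0.1266, 0.25, 0.3997, 0.5421 with a one-parameter logistic model (intercept 3), which rounds to the printed values. With the power model it gives 0.043, 0.124, 0.25, 0.398, 0.542, within 0.01 of print. The printed values are used below.

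**2. Model.** p_i = s_i^b, where s_i is the skeleton value. The estimate of b maximises Σ[y_i log p_i + (n_i − y_i) log(1 − p_i)]. The recommended level has p_i nearest 0.25.

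**3. Path A (down from level 3).**
- Level 1 0/3, level 2 1/3: the model stays at level 2, and 1/3 = 33.3% bars level 3 in any case.
- A fourth level 2 patient without DLT (1/4 = 25%): b = 1.260, estimates 17.4% at level 2 and 31.5% at level 3. The distances from 25% are 7.6 and 6.5 points, so level 3 opens.
- Level 3 3/3: b = 0.732.

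**4. Path B (down from level 2).** Level 1 0/3, level 2 3/3: b = 0.444.

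**5. Path C (down from level 4).** 0/3, 0/3, 0/3 at levels 1 to 3, then 6/6 at level 4: b = 1.062.

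| Path | Estimates | Model recommends | Stratum 2 literal text |
|---|---|---|---|
| A | L0 11.2%, L1 22.4%, L2 36.2%, L3 51.1% | level 1 (22.4%) | level 2 (36.2%) |
| B | L0 26.5%, L1 40.5%, L2 54.1% | level 0 (26.5%) | level 1 (40.5%) |
| C | L2 22.9%, L3 37.8%, L4 52.0% | level 2 (22.9%) | level 3 (37.8%) |

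The 33% restrictions do not intervene. The intermediate level stands at 1/4 (25%), 0/3 and 0/3 respectively, and no level below it has reached 33%. The unrounded skeletons give the same recommendation in path B (about 40% at level 1, 25-27% at level 0). When the level nearest 25% can be used and is not the lowest, its estimate never exceeds about 32% (maximum 0.321). Above the lowest level, then, the excess comes from the no-skip wording.

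**6. Frequency in a trial starting afresh.** The documents give no true DLT rates, so these are assumptions. The chance of path B alone is (1 − π1)³ × π2³:
- skeleton true (13%, 25%): 0.87³ × 0.25³ = 1.0%
- one level more toxic (25%, 40%): 0.75³ × 0.40³ = 2.7%
- steep at level 2 (10%, 50%): 0.90³ × 0.50³ = 9.1%

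Simulating the whole Stratum 2 algorithm (20,000 trials, cohorts of 1 or 3 at revisited levels), any forced assignment above 32% occurs in about 2-4%, 5-6% and 14-16% of trials respectively. With a less toxic curve it is below 2%.

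**7. Remaining effect at the reported stage.** Section 13.2 (update for version 8) reports level 3 declared too toxic, a step down to level 2, six treated there and three at level 1. A skip would now have to run from level 2 to level 0. DLT counts are not reported. Assume 0-1/3 at level 1, 0-1/6 at level 2, 33-67% DLTs among 6 to 24 patients at level 3, and a current recommendation of level 2. At least five DLTs in the next five or six level 2 patients would then be needed. Example: 0/3, 1/6, 4/9 gives level 2 (21.0%). Six more DLTs in six (7/12) gives b = 0.624 and estimates of 15.4%, 28.0% and 42.1% at levels 0 to 2, so the model recommends level 1, which is adjacent and needs no skip.

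**8. Pending limit.** Section 13.2 projects 1-2 patients per month. Assuming Poisson arrivals and a 28-day window, four or more are pending about 1.5% of the time at 1 per month and 12% at 2 per month. Six or more are pending about 0.04% and 1.2% of the time.

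**The case against.** The strongest reply is that this is only a dropped qualifier. A reader might infer that the Stratum 2 clause cannot mean escalation alone, since the first bullet already covers escalation. Stratum 1 shows otherwise: it has the same first bullet and still repeats no-skip in the later bullet, expressly for escalation. The introductory sentence about caution when escalating points the same way. This stands, and it makes an omission the likelier explanation. It does not make the printed rule correct.

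Three further points also stand. Stratum 1 permits downward skipping but does not require it. The 18-32% interval calibrates which dose is acceptable as the MTD and is not a stated ceiling on interim assignments. The documents report only a one-level step down in Stratum 2, so nothing shows that the clause has ever bound.

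On pending evaluations, a reader might infer that losing the cap sends children to levels above 32%, or exposes a whole expansion cohort before any review. The documents support neither. The cap does not choose the level, and a conditional exception stands in its place, so the change may be deliberate. Expansion DLTs are to be monitored in the same way as before, the 33% restriction still closes a level, and each enrolment needs a reserved slot (Sections 4.2.1 and 4.3). Six pending at once is very unlikely at the projected accrual. What remains is that none of these provisions gives a number for revisited levels or the expansion.

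**Conclusion.** The point holds as an inconsistency between the strata with a demonstrable consequence. Followed literally, the Stratum 2 clause can assign a level with an estimated DLT rate of 36-41% when the model recommends one at 22-27%, and neither 33% restriction stops it. The examples depend only on the printed skeleton, the power model and the target. The frequencies (about 2-6% of fresh trials, below 2% if toxicity is milder, 14-16% if steep) depend on assumed true rates. At the stage reported in Section 13.2 the clause would bind only after an extreme run of DLTs, under assumed counts. It should therefore be corrected as a rule, not reported as a harm that has occurred. The missing pending limit is a request for clarification and plays no part in the result above 32%.

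**What to change.** 1. Reconcile the two lists in Section 13.1.2: limit the Stratum 2 no-skip restriction to escalation and carry over the Stratum 1 sentence on de-escalation, or state why Stratum 2 differs.
2. State whether the limit of three pending DLT evaluations was deliberately removed for Stratum 2, and what limit, if any, applies at revisited levels and in the expansion cohort.

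The first change takes one condition and one sentence in an amendment and needs no extra patients. The second is a sentence of clarification. If a cap of three were kept, the cost in accrual would be modest but not nil: under the Poisson assumption above, three or more are pending about 7% of the time at 1 patient per month and 28% at 2 per month.
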